## 1. Introduction and Purpose:

Nearly 70% of the 13 million people living with cancer are “complex cancer survivors” who are also dealing with multiple other chronic conditions. The prevalence of complex cancer survivors is expected to continue growing because successful treatments result in longer survival and cancer diagnoses occur most often in older persons who are more likely to have multiple chronic conditions. The National Comprehensive Cancer Network (NCCN) emphasizes that managing survivors’ needs includes caring for their other chronic conditions. These complex patients need highly coordinated care to ensure optimal outcomes for their cancers, co-existing chronic conditions, and overall quality of life, but no effective models for doing this exist.

**This project is a pragmatic trial.** We propose a quasi-experimental design where data will be collected both pre- and post-intervention on distinct cross-sections of patients with one or more highly prevalent ambulatory-sensitive chronic conditions (diabetes, hypertension, chronic lung disease, chronic kidney disease, depression, or heart disease) and newly diagnosed with breast or colorectal cancers (complex cancer survivors) in the Parkland Health & Hospital system (Dallas, TX). Guided by the *Primary Care Change Model*, Parkland will implement evidence-based care coordination strategies to improve care for complex cancer survivors in this integrated safety-net system as a part of quality assurance/quality improvement activities (Aim 1), then this study will comprehensively evaluate how these strategies are implemented in the safety-net setting (Aim 3), and whether implementing these strategies improves care coordination and care outcomes (Aim 2) within the Parkland Health and Hospital System.

## 2. Background:

**Following initial cancer treatment, needs of complex cancer survivors are not well met, resulting in poor health outcomes.** Management of a new cancer diagnosis often interrupts existing chronic disease care because patients undergo intensive oncology care for an extended period of time during which attention to their other conditions may wane. Further, patients with cancer often continue to be followed by oncologists after completion of initial treatment with little or no care coordination with primary care clinicians. Thus, care is fragmented and the providers siloed, resulting in suboptimal care quality. **The Institute of Medicine (IOM) argues a lack of system-level approaches to navigate survivors between primary and oncology care contributes to fragmentation and poor outcomes.** This is further complicated by ineffective use of clinical decision support tools (disease registries, alerts, referral tracking) and fragmented care delivery approaches. Effective care coordination organizes patient care activities and provider information-sharing to facilitate shared-care and appropriate service delivery.

**The burden of cancer, multiple chronic conditions, and fragmented care is greatest among under-and uninsured minority patients.** For example, nationally, African Americans have worse quality-of-care outcomes on 73 preventive and chronic disease care indicators. **Similar disparities in quality-of-care outcomes exist particularly for cancer survivors** who are racial/ethnic minorities, uninsured, and receiving care in safety-net health systems. **At Parkland Health & Hospital System (Parkland)-Dallas County’s integrated safety-net system - 72% of cancer patients are racial/ethnic minorities, 70% are uninsured, and more than 60% have three or more chronic conditions.**

Parkland preliminary data show only 43% of colorectal cancer survivors met guidelines for both cancer surveillance and appropriate diabetes care. Our application proposes innovative research to improve care for this vulnerable group of patients.

Despite a significant body of evidence regarding best strategies to improve care for patients with multiple chronic conditions, there is little research on complex cancer survivors. The IOM, Agency for Healthcare Research & Quality (AHRQ), and Institute for Healthcare Improvement all support care coordination as a mainstay of interventions to improve care quality for complex patients. The 2007 AHRQ report, synthesizing 75 systematic reviews of care coordination interventions along with more recent research, shows that strategies with compelling evidence for improved outcomes include: (1) EMR-driven transitions using alerts and referral tracking; (2) intensive case management; and (3) team-based care. These strategies improve transitions in care processes, enhance continuity, reduce lack of follow-through on referrals, and ensure that patients receive all recommended care through regular information-sharing. They also demonstrate improved patient experience of care and clinical outcomes. Further, care coordination interventions conducted in integrated systems like Parkland – where primary and specialty care communicate through a common electronic medical record system (EMR) – have the greatest potential for improving outcomes. Evidence for effectiveness of case managers and automated reminders originated in insured integrated systems and have shown improvements in diabetes performance measures and cancer screening. Also, care coordination interventions among elderly patients with multiple chronic conditions show improved outcomes compared with those focusing on a single disease.

Although there is sufficient evidence for using these strategies for common medical conditions in primary care, their effectiveness in coordinating care for complex cancer survivors has not been evaluated. Therefore, in Aim 1, Parkland will implement these care coordination strategies for complex survivors as a part of quality assurance/quality improvement, and Aim 2 and Aim 3 will evaluate these strategies. We will use mixed methods to comprehensively evaluate implementation of care coordination strategies among complex cancer survivors at Parkland. We use the empirically informed *Primary Care Practice Change Model* to guide our evaluation design. This intervention mixed-methods evaluation will examine not only *whether* the selected strategies were effective, but also *how* and *why* they worked (or did not work) is critical to generating transportable findings necessary for broader dissemination.

### 3. Study Procedures:

We expect approximately 1000 new survivors with  $\geq 1$  prevalent chronic condition to be eligible. We will not include patients diagnosed with *in situ* and metastatic disease (Stages 0 and IV) due to insufficient evidence for routine follow-up and management; many of the latter continue indefinitely on active treatment for symptom management. The chronic conditions we selected for inclusion are the most prevalent conditions cancer survivors have at Parkland as well as nationally.

**Aim 1: (Quality assurance/quality improvement) Parkland will implement system-level EMR-driven evidence-based care coordination strategies; (1) EMR-driven registry to facilitate patient transitions between primary care and oncology care, (2) co-locate a nurse practitioner trained in care coordination within a complex care team, and (3) enhance teamwork through coaching and technical assistance.**

- **Strategy 1:** Using the Epic Reporting Workbench, Parkland EMR data will be extracted in order to create a registry of complex cancer patients to facilitate transitions primary care and oncology care.
- **Strategy 2:** During Year 1 of this study, Parkland will educate clinicians and staff about the proposed system change and train primary care physicians on ways to identify and refer survivors to the complex care team. Parkland will designate a new complex care team for

eligible patients. This team will be housed within a Parkland community oriented primary care clinic. Due to the acuity and complexity of the needs of complex cancer survivors, the team will be staffed by a primary care physician and a nurse practitioner, and will include an RN/LVN nurse, a medical assistant, a social worker, and a mental health counselor.

- **Strategy 3:** Parkland will map team workflow around all aspects of delivering care to complex cancer survivors, establishing team goals, train team members in all aspects of cancer survivorship care including providing booster training sessions and coaching, enhance communication, set ground rules to make decisions, and finally pro-actively create standing orders to empower non-physician team members to share care delivery. Parkland will facilitate primary care teams in developing systems needed to enhance teamwork and implementing incremental practice change initiatives through quality improvement cycles.

**Aim 2: (Research Component)** *Test effectiveness of the care coordination strategies using a quasi-experimental study, with system- and patient-level outcomes measured before and after implementation.*

**System-level hypothesis:** The primary outcome is proportion of complex cancer survivors meeting quality of care guidelines for multiple chronic conditions and follow-up cancer surveillance. We will use clinical care guidelines for chronic disease care and *National Comprehensive Cancer Network* (NCCN) guidelines for cancer surveillance to determine if patients are eligible for services. We will also determine whether patients received guideline-appropriate cancer surveillance, e.g., whether colorectal cancer patients received CEA testing every 6 months, endoscopy surveillance, and CT scans annually. We will also measure rates of ED and hospitalizations (secondary outcomes) for ambulatory care-sensitive chronic conditions at the same time points as the primary outcomes. The outcome measure will be derived from quality scores for: (a) chronic disease care and (b) cancer follow-up care. We will create these scores by, first, determining for each patient the percentage of eligible guideline-recommended services received and clinical targets met, then, calculating the percentage of patients that met 100%, 75%, and 50% of these indicators. The 75% and 50% composites are less stringent and assess percentage of patients who achieved success on fewer indicators. Finally, we will calculate a composite overall care score that includes both chronic disease and cancer follow-up score. Computing composite scores will allow us to measure not only changes separately in chronic disease care and cancer follow-up care but also changes in overall care. This extends current research beyond single-disease measures to focus on overall care quality.

**Patient-level hypothesis:** **Patient-reported care coordination assessed via Patient Perception of Care Scale**, which has been validated in primary care and is associated with improvements in reported problems with care coordination. We will use the EMR-generated registry to randomly select 866 complex cancer survivors to survey 402. Surveys will be administered three times by phone – once prior to their initial visit with the complex care team (baseline) and twice thereafter at 6 and 12 months. Prior to fielding surveys, we will conduct 15 cognitive interviews (with patients who will be excluded from the larger project) to ensure measures not already validated in Spanish are adapted for language, literacy and culture.

**Aim 2 Statistical analyses:** We will use segmented logistic regression and linear mixed regression models to assess effect of care coordination strategies on system and patient outcomes.

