**To evaluate system-level hypotheses, the design is a repeated cross-sectional study with outcomes**

measured for distinct cross-sectional samples of patients at five points. To analyze these data, we will first use chi-square tests to compare proportion of eligible patients meeting guidelines at 12 and 24 months before implementation to proportion of patients meeting guidelines 12, 24 and 36 months after system-level strategies are in place. We will then use segmented logistic regression models to identify the time point at which observed trend in proportion of patients meeting guidelines. We expect a significant p-value for change in proportion of patients meeting guidelines after implementation of system-level strategies. Conversely, we expect the trend for proportion of patients meeting care guidelines before implementation to be stable with a larger p-value. This trend, in conjunction with additional qualitative information gathered about implementation (Aim 3), will provide evidence that implemented strategies resulted in changes in outcomes.

**Power/sample size:** To demonstrate a minimum increase of 10% in the primary outcome after implementation of system-level strategies as compared to before implementation, a sample of 170 patients at each time point will provide 80% power at the 0.05 significance level based on the chi-square test for comparing proportions. We have many more patients than needed; as system-level outcomes will be evaluated using EMR data, we will include all eligible patients and conduct subgroup and sensitivity analyses to better characterize effects.

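### The system-level pass rate depends on how many indicators each patient is eligible for, but the before-after analyses compare different patients and name no case-mix covariates

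*Combined protocol and SAP*

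**What the plan says.** Section 3, Aim 2 (system-level hypothesis), builds the outcome by "determining for each patient the percentage of eligible guideline-recommended services received and clinical targets met". That patient-level score is turned into a pass rate at three cut-offs, by "calculating the percentage of patients that met 100%, 75%, and 50% of these indicators". No threshold is named as primary. Section 4 admits patients with either of two cancers and at least one of six chronic conditions, so the set of eligible indicators differs between patients.

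The design has outcomes "measured for distinct cross-sectional samples of patients at five points". On the analysis, the plan says "we will first use chi-square tests to compare proportion of eligible patients meeting guidelines at 12 and 24 months before implementation" with those at 12, 24 and 36 months afterwards. The next step reads "We will then use segmented logistic regression models to identify the time point at which observed trend". No covariate, stratification or weighting is given for either step. The power statement is tied to the first step: "a sample of 170 patients at each time point will provide 80% power at the 0.05 significance level based on the chi-square test".

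Some protection is planned:
- The Aim 2 overview gives the segmented model an inferential role: "We will use segmented logistic regression and linear mixed regression models to assess effect of care coordination strategies".
- Chronic-disease and cancer scores are also reported separately.
- The plan adds "we will include all eligible patients and conduct subgroup and sensitivity analyses to better characterize effects", without stating their content.
- Aim 3 looks for other explanations of any observed effect.
- Control of confounding is mentioned for the patient-level mixed model, also without a covariate list.

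**The concern.** Meeting every indicator is harder with eight indicators than with four, even if care per indicator is identical. If the share of patients with many indicators differs between the periods, the pass rate moves although care has not. Depending on direction, that can look like a benefit or hide part of a real one. There is no randomisation and no concurrent control for this comparison, so measured case mix is the part of the problem that analysis can address. A chi-square test cannot carry covariates, and it is the analysis on which the stated power rests.

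**Working it through.** **Inputs.** From the documents: 170 per time point, two pre and three post points, a 10% increase (read as 10 percentage points), alpha 0.05 (taken as two-sided). The 43% baseline is the preliminary figure in Section 2, which concerns colorectal survivors and diabetes care only; the power paragraph gives no baseline. Assumed, because the documents give none: 60% of patients have 8 indicators and 40% have 4; within-patient correlation between indicators is 0 to 0.2; no change in care per indicator.

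**1. The plan's power figure.** With s0² = p̄(1−p̄)(1/n1+1/n2) and s1² = p1(1−p1)/n1 + p2(1−p2)/n2, power ≈ Φ((|p2−p1| − 1.96·s0)/s1).
- Pooled, 340 v 510, 43% v 53%: 81.7%, close to the stated 80%.
- One point against one, 170 v 170: 45.4%.

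So 170 per point fits the pooled reading at a baseline near 43%. That reading is inferred, not stated.

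**2. Pass rates by indicator count.** Solve 0.4·P4 + 0.6·P8 = 0.43.
- Independent indicators: success rate 0.871, P4 = 0.871⁴ = 0.576, P8 = 0.871⁸ = 0.332.
- Correlation 0.2 (beta-binomial): success rate 0.804, P4 = 0.523, P8 = 0.368.

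**3. Bias from a step in mix.** If the 8-indicator share falls by s, bias = s·(P4−P8), where P4−P8 is 0.244 or 0.155. False-positive rates use the formula in step 1 and were checked in 5,000 simulated trials. Power under an opposite shift is from the simulation.

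| Step in mix | Bias (points) | False-positive rate | Power for a true 10-point gain if the shift is opposite |
|---|---|---|---|
| 5 points | 0.8-1.2 | 6-7% | 72-76% |
| 10 points | 1.5-2.4 | 7-11% | 58-68% |
| 20 points | 3.1-4.9 | 14-29% | 31-50% |

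Example, 20 points under independence: p2 = 0.479, s0 = 0.0349, s1 = 0.0348, so (0.0488 − 0.0684)/0.0348 = −0.56 and Φ = 0.29.

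**4. Segmented model.** Times are −2, −1, 1, 2 and 3 years. The level change from 43% to 53% is 0.402 on the logit scale. Its standard error from the information matrix is 0.369 with a common slope and 0.418 with a slope change, giving power of 19% and 16%. Under a 20-point step its false-positive rate is 6-8%. Under gradual drift in the 8-indicator share from 60% to 40% it stays at 5%, while the chi-square gives 10-17%.

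**5. Other thresholds.** In the 8 v 4 example a 20-point step moves the 75% and 50% measures by −0.2 to 0.8 points. With 3 v 6 indicators and success rates of 0.75 to 0.90, it moves the 100% measure by 4.0 to 5.0 points, the 75% measure by −2.2 to −3.2 and the 50% measure by −0.5 to −2.4.

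**6. How much adjustment recovers.** Suppose the covariates classify patients into the 8- or 4-indicator group with 90% accuracy, and the 8-indicator share steps from 60% to 40%. Among patients classified as 8, the true share goes from 0.54/0.58 = 0.931 to 0.36/0.42 = 0.857; the other group also changes by 0.074. Residual bias is 0.074 × 0.244 = 1.8 of 4.9 points. At 80% accuracy the change is 0.130 and the residual 3.2 points.

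**7. Cost in power.** Multiply the effective sample by 1−R², where R² is the assumed correlation of period with covariates. For R² of 0.05, 0.10 and 0.20, power at 170 per point is 79.7%, 77.5% and 72.6%. At 200 per point (about 1000 eligible patients spread evenly, an assumption) it is 85.7%, 83.8% and 79.3%.

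**The case against.** The plan never calls the chi-square the main analysis. The Aim 2 overview gives the effect assessment to the segmented model, and the interpretation rests on the trend together with Aim 3. The large false-positive rates apply to the first-step test only. This stands, and it is why the segmented model should not be demoted. A reader might go further and infer that an adjusted pooled pre/post comparison should become the primary analysis. The documents do not support that. The mean pre and post times are 3.5 years apart (−1.5 to 2), so a background improvement of 1 or 2 points a year (assumed) would bias the pooled term by 3.5 or 7 points, with 17% or 52% false positives. Case-mix covariates would not remove it.

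The sizes also rest on assumptions. Nothing in the documents points to a 20-point step in one health system under fixed eligibility criteria, and a 5-point step does little harm. This too stands.

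The separate scores and the unspecified sensitivity analyses help less. The chronic-disease denominator still varies with the number of conditions, and an analysis without stated content cannot be relied on to include adjustment. Aim 3 can help to explain a biased estimate but does not correct it.

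**Conclusion.** The point holds as a gap in the planned analysis: the denominator is patient-specific, the patients differ between periods, and neither system-level analysis names case-mix covariates. The distortion at the 100% threshold is about 1 to 5 points for a 5- to 20-point step in mix, against a 10-point target. That is conditional on the assumed indicator counts, the 43% baseline, within-patient correlation of 0 to 0.2 and the pooled reading. Effects at 75% and 50% are smaller and can go either way. The segmented model is fairly robust but, at 16-19% power for the level change, cannot stand in for the before-after comparison.

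Two stronger readings should be avoided. A reader might infer that the trial's result will be biased; the documents show no shift in mix and do not fix its direction. A reader might also infer that adjustment makes the comparison unbiased at no cost; steps 6 and 7 of the working show otherwise. The change is worth making, with medium confidence in the sizes.

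**What to change.** 1. Base before-after inference on a logistic model with a pre/post term, adjusted for pre-specified cancer type, stage, age and grouped chronic conditions, and reported as a standardised difference. Keep the chi-square as descriptive. Where dates allow, use conditions recorded before the cancer diagnosis, with the same look-back in both periods, because the registry and care team in Aim 1 may change what is recorded.
2. Add the same covariates to the segmented logistic model and keep its planned role, since the pooled term cannot separate the intervention from a background trend. State its power.
3. Tabulate eligible-indicator counts at the five time points. Add two sensitivity analyses: one adjusting for the number of eligible indicators, and one fixing each patient's denominator from pre-diagnosis conditions. The second is needed because new recording changes the denominator itself. If 10% or 20% of 4-indicator patients gain four indicators after implementation, the bias is 0.4 × f × (P4−P8), or 0.6-1.0 or 1.2-2.0 points, and adjustment on pre-diagnosis conditions does not remove it.

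**Cost.** Mainly plan wording and modest extra analysis. Section 6 lists demographics, cancer and comorbidity diagnoses and treatment data in the extract, but does not state dates for comorbidity diagnoses. Pre-diagnosis records may be incomplete for some patients, and look-back is short for those diagnosed soon after 01/01/2010. Sparse conditions must be grouped. Imperfect covariates leave part of the bias, and power at 170 per point may fall to about 73-80% if case mix is correlated with period.

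### The primary system-level outcome is defined in words, but no score, cut-off or time-point contrast is designated for it and no multiplicity rule is stated

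*Combined protocol and SAP*

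**What the plan says.** All references are to the combined protocol and SAP, section 3 (Study Procedures), Aim 2, unless stated.

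- **Outcome in words** (system-level hypothesis): "The primary outcome is proportion of complex cancer survivors meeting quality of care guidelines for multiple chronic conditions and follow-up cancer surveillance". This is singular and joins both domains. The same paragraph later uses the plural when it refers to the primary outcomes. Only emergency department visits and hospitalizations are labelled secondary.
- **How it is measured** (same paragraph): a chronic disease score and a cancer follow-up score, then "calculating the percentage of patients that met 100%, 75%, and 50% of these indicators". On the lower cut-offs: "The 75% and 50% composites are less stringent and assess percentage of patients who achieved success on fewer indicators". On the composite: "Finally, we will calculate a composite overall care score that includes both chronic disease and cancer follow-up score". No cut-off is attached to the composite.
- **Chi-square tests** (system-level analysis): "we will first use chi-square tests to compare proportion of eligible patients meeting guidelines at 12 and 24 months before implementation" with 12, 24 and 36 months afterwards.
- **Segmented regression.** The Aim 2 statistical analyses summary says "We will use segmented logistic regression and linear mixed regression models to assess effect of care coordination strategies on system and patient outcomes". The system-level paragraph says "We will then use segmented logistic regression models to identify the time point at which observed trend in proportion of patients meeting guidelines", and the sentence ends there without completing its thought.
- **Safeguard** (system-level analysis): "Conversely, we expect the trend for proportion of patients meeting care guidelines before implementation to be stable with a larger p-value", to be read together with the qualitative evidence from Aim 3.
- **Power** (Power/sample size): 170 patients per time point, 80% power, 0.05 level, chi-square test, minimum increase of 10%. Baseline rate, sidedness and absolute or relative increase are not given.

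The document contains no testing hierarchy, alpha split or multiplicity adjustment.

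**The concern.** The plan explicitly builds six measures (two domains at three cut-offs), and a seventh if the overall composite is read at 100%. Each can be tested at 0.05, on a pooled contrast or on any of 2 x 3 = 6 before/after pairs. Nothing in the text prevents primary success from being reported on a lower cut-off, on one domain or on one favourable pair, chosen after the results are seen.

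The contrast also decides what the power statement means, because 170 per point is adequate under one reading and, at most baselines, well short under the other.

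Finally, the system-level comparison has no concurrent control. A before/after chi-square cannot separate an intervention effect from a drift over time. That job falls to the segmented model, whose stated role is left incomplete, and to a pre-implementation trend resting on two points.

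**Working it through.** **Inputs.** From Power/sample size: 170 per point, 0.05, 80%, 10% increase. From the system-level analysis: two points before, three after. Assumed, because not stated: two-sided test and an absolute 10-point rise. Baseline 43% is borrowed from section 2 (Background), where it covers colorectal survivors and diabetes care only, so a range is shown.

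**1. The plan's own figure.** Power = Φ[(d − 1.96·SE0)/SE1], where SE0 = √[p̄(1−p̄)(1/n1+1/n2)] and SE1 = √[p1(1−p1)/n1 + p2(1−p2)/n2].

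- *Pooled*, n1 = 2 x 170 = 340, n2 = 3 x 170 = 510, 43% to 53%: p̄ = 0.49, SE0 = 0.0350, SE1 = 0.0348, z = (0.10 − 0.0686)/0.0348 = 0.90, power **81.7%**. The minimum over baselines 1% to 89% is **81.6%**. The size required at 43% is 163 per point, or 172 with continuity correction, so 170 is reproduced under pooling.
- *One pair*, 170 vs 170, 43% to 53%: p̄ = 0.48, SE0 = 0.0542, SE1 = 0.0539, z = (0.10 − 0.1062)/0.0539 = −0.12, power **45.4%**. It is 56.8% from a 20% baseline and 81.3% from 7%. A pair reaches 80% only at baselines up to about 7.4% or from about 82.6%.

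**2. Chance of a false improvement.** Null simulation with five samples of 170 and 4,000 trials in each of 36 assumed settings: propensity SD 0.5, 1 or 2 on the logit scale; domain correlation 0.3 or 1.0; three patterns of indicators per patient; indicator pass rate 0.6 or 0.8. One pooled test was run per measure, and any significant improvement was counted as success.

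| Measures tested | False improvement | Also requiring that measure's two pre points not to differ (p>0.05) |
|---|---|---|
| Overall at 100% only | 2.1-2.9% | 2.0-2.8% |
| Six (two domains, three cut-offs) | 8.4-12.9% | 8.0-12.4% |
| Seven (six plus overall at 100%) | 9.1-14.1% | 8.8-13.6% |

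As a guide, independent measures would give 1 − 0.975^6 = 14.1% and 1 − 0.975^7 = 16.2%; correlation puts the simulated values below these. The last column changes little partly by construction: with no trend, the pre-point check passes about 95% of the time. One measure tested over the six pairs gives 8.6-12.4%.

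**3. The pre-trend check.** Assume no intervention effect and a rise of 2 points a year from 43%, at times −2, −1, 1, 2 and 3 years. The rates are 43, 45, 49, 51 and 53%, averaging 44% before and 51% after. At 170 per point the pooled chi-square rejects 52% of the time, and the two pre points differ significantly only about 7% of the time. A segmented logistic model (linear trend plus level change) rejects 4.9% of the time.

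**4. Precision of the segmented model.** For a step from 43% to 53%, the level change is logit(0.53) − logit(0.43) = 0.120 + 0.282 = 0.402. Its standard error from the five-point design is 0.369 at 170 per point, so z = 1.09 and power is about Φ(1.09 − 1.96) = **19%**. At 200 per point the standard error is 0.340 and power about **22%**. For 10% to 20% at 170 it is about 38%.

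**The case against.** The strongest reply is that the plan is less open than this suggests. The primary outcome is singular and joins both domains; the domain scores are inputs to it; the lower cut-offs are called less stringent; and the paragraph closes on overall quality of care. The power sentence reads naturally as before against after. Pairing at a 43% baseline would need 391 per point, or 5 x 391 = 1,955 patients, against about 1,000 expected. All of this stands, but it is inference: no sentence designates the measure or the contrast, and the plural use cuts the other way.

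Several stronger readings are tempting and are not supported:

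- *That 170 is wrong.* Under pooling it suffices at every baseline from 1% to 89%, so the missing baseline is a matter of transparency there. All eligible patients will be included, so 170 is a minimum. An even split of about 1,000 would give 200 per point and, at 43%, pooled power of about 87% (400 vs 600).
- *That there are nine rival primary measures, or an error rate of 20-30%.* Nine requires three cut-offs for the overall score, which the text does not state. Rates that high count false deteriorations, whereas the plan seeks an increase.
- *That the plan will claim any p<0.05.* It neither states nor excludes this. It also expects a stable pre-trend and qualitative support; the latter is not modelled and could lower the rates.
- *That the two descriptions of the segmented regression contradict each other.* Locating a change can be part of assessing an effect. The defect is an unfinished sentence.

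Drift over time is a separate matter that naming one measure does not cure. It bears here on what a significant chi-square may be said to show. Designating a 75% measure would equally remove the multiplicity; 100% is suggested because it is closest to the plan's wording.

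**Conclusion.** The point holds in limited form, as a cheap improvement. The plan leans to the overall composite at 100% and to a pooled contrast but designates neither, and it gives no multiplicity rule. Under the any-significant-improvement assumption, at 170 per point and with assumed indicator structures, this raises the chance of a false improvement from 2-3% to about 8-14% for six or seven measures. The sample size is supported if points are pooled and, away from extreme baselines, not if they are paired. A non-significant difference between two pre-implementation points is weak evidence of stability. Confidence is medium, because pass rates, correlations and the claim rule are not in the document.

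**What to change.** Make these changes before outcome data are analysed.

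1. **System-level hypothesis paragraph.** Designate one primary measure; the overall composite at 100% is closest to the existing wording. Make the other cut-offs and the two domain scores secondary, reported as estimates with 95% confidence intervals.
2. **System-level analysis and power paragraphs.** State that the powered test is one chi-square of pooled before (12 and 24 months) against pooled after (12, 24 and 36 months) at two-sided 0.05, with time-point pairs descriptive. State the assumed baseline and that the 10% is absolute, if that is what is meant.
3. **Segmented regression.** Complete the sentence: on the same measure, report the level change at implementation, allowing for the pre-implementation trend, with its 95% confidence interval and expected precision.
4. **Interpretation.** Say that a significant chi-square alone shows a before/after difference, and that a non-significant two-point pre-trend does not show stability. If the chi-square is significant and the segmented estimate inconclusive, the conclusion is a before/after improvement with attribution unproven.

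**Cost.** Wording and one precision statement; no new data. The sponsor gives up primary claims on lower cut-offs, single domains or single pairs. It must also disclose that the segmented model is imprecise (about 19% power for 43% to 53% at 170 per point, about 22% at 200), so a non-significant segmented result is inconclusive and not evidence of no effect.
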